Hypothesis 1: There will be a greater reduction in the Neurobehavioral Symptoms Inventory (NSI) from pre- to post-SAET compared to the control condition. A similar finding will continue from immediate to 3 month post-SAET.

Secondary Aims:

Sub-aim 1 Cognitive Status: To determine if SAET is effective at improving cognitive impairment among SMs with persistent complaints from mTBI.

Sub-hypothesis 1: There will be a greater decrease in the Global Deficit Scores (GDS; an overall measure of cognitive impairment) post SAET in comparison to the control condition.

Sub-aim 2 Physiological Adaptation: To measure physiological adaptation associated with SAET compared to the control condition.

Sub-hypothesis 2: SAET will be associated with improved cerebrovascular blood flow regulation, as measured by Transcranial Doppler and improved cardiovascular function, as measured by changes in heart rate variability (HRV) and estimated maximal oxygen consumption (est. VO₂ max) compared to the control condition.

Sub-aim 3 Warfighter Performance: To determine if SAET participants will have improved locomotion and a higher level of occupational performance compared to the control condition.

Sub-hypothesis 3: SAET participants will have improved locomotion and physical performance (based on the Marine Corps Combat Fitness Test(CFT)) and higher ratings of occupational performance (based on supervisor ratings on the Checklist of Military Activities of Daily Living [M-ADL]) after completion of treatment and 3 months post-treatment compared to the control condition.

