10.0 Study Procedures, Data Management, and Privacy

10.1 Study Procedures

Describe step-by-step how the study will be conducted from beginning to end

Individuals who report interest in the study and report a history of at least one previous TBI, as well as persistent symptoms they believe to be related to that injury, will be enrolled in the study

(see **Figure 1**). Participants will complete a short screen for inclusion and exclusion criteria as dictated for this study. After screening and consenting, participants will be randomly assigned to one of two study arms, the sub-symptomatic adaptable exercise treatment (SAET) treatment group or the stretching control group (SCG) control group, and given a pre-study evaluation to capture baseline functioning. Participants will then be scheduled to begin the study intervention and will receive appointment reminders via phone, text, and/or email. For each participant, randomized to SAET or SCG, additional evaluations will be completed following their last treatment session and at 3 months post-treatment. **Figure 2** details the study procedure timeline.

Participants will be randomized into either the exercise or the stretching condition group in a 1:1 fashion within a block size of 6, which will be utilized until all potential participants are assigned to a group (70 in exercise group and 70 in stretching condition group). Halfway during recruitment, the sample size will be reassessed for balance between the two groups. If needed, adjustment of randomization, for example, to a 2:1 ratio, will be conducted but maintaining the block size of 6. Periodic adjustment may be necessary to obtain the minimum sample size for this project. The study biostatistician will conduct randomization and an assignment schedule will be provided to the project coordinator who will keep such schedule under a password-protected encryption.

Study Evaluations

Participants will undergo the following assessments and evaluations at three study time points: pre-, post-, and 3 months post-treatment.

Cognitive Assessments

Participants will undergo various neuropsychological assessments and complete self-report measures administered via paper and pencil or electronically using an approved data collection platform. Cognitive assessments will take approximately 1 hour to administer at each time point, pre-, post-, and 3 months post-treatment. Specific assessments are described below in Section 10.2.

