11.0 Statistical/Data Analysis Plan

11.1 Statistical Considerations:

List the statistical methods to be used to address the primary and secondary objectives, specific aims, and/or research hypotheses. Explain how missing data and outliers will be handled in the analysis. The analysis plan should be consistent with the study objectives. Include any sub-group analyses (e.g., gender or age group). Specify statistical methods and variables for each analysis. Describe how confounding variables will be controlled in the data analysis

1. Data Analyses

The difference between treatment groups sample characteristics including demography, military information and co-variates will be evaluated using Student's 't' and chi-square tests for continuous and categorical variables, respectively. Wilcoxon Rank-Sum test will be used for two-group comparisons where continuous variables are non-normally distributed. We will leverage the statistical power of multilevel modeling to handle missing follow-up data.

Please see section 11.6 for the data analysis plan.

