11.5 Please provide a justification for your sample size

With 140 participants, 70 in each intervention arm, we will be able to potentially detect a significant difference in change in neurobehavioral symptoms between the two physical activity interventions (i.e., SAET and SCG) with an 85% power using a two-tailed test and an alpha of 0.05. This estimate is based on similar research on a civilian population (Kaplan, Vasterling, & Vedak, 2010), and takes into consideration a 20% attrition. The 140 participants recruited will suffice to address the research question for secondary aims given the same parameters.

11.6 Data Analysis Plan Complete description: Background, Objectives, Design, Step by Step how the project is going to be done

Primary Aim: Neurobehavioral symptoms: Primary analyses will evaluate whether change in neurobehavioral symptoms from pre- to immediate post-treatment, as well as from immediate post-treatment to 3 months post-treatment, differ between the physical activity interventions. In addition to assessing change in symptoms continuously, we will also evaluate reaching a clinically-relevant change in neurobehavioral symptoms (defined as a change in NSI score of 8 points) (Belanger et al., 2016). Secondary analyses will investigate differences in overall change in neurobehavioral symptoms from pre-treatment to 3 months post-treatment between the interventions using multilevel mixed-effect modeling. This approach will take into consideration between-subject variance based on randomized group, as well as within-subject variance for repeated measures. Analyses will be based on intention to treat (ITT).

Sub-Aim 1: Cognitive Performance: Similar statistical approach as Aim 1 will be conducted for Sub-Aim 1. Exposure will remain as the type of intervention (i.e. SAET vs. SCG); however, outcome will be on global deficit score based on the cognitive test scores.

Sub-Aim 2: Physiological Adaptation: Analysis of Variance (ANOVA) will be utilized to determine differences in continuous variables of physiological adaptation (i.e., cerebrovascular flow, improved cardiovascular health) between interventions.

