Sub-Aim 3: Warfighter Performance: ANOVA will be utilized to determine differences in M-ADL scores between interventions. As described in Table 3, participants will be categorized as passing or not passing their CFTs. As such, given >10% with passing CFTs, we will utilize Poisson regression with robust error variable to determine the prevalence ratio of passing CFTs between the physical activity interventions.

A significant p-value of 0.05 will be used to assess main effects.

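### Sub-Aim 2 outcomes and M-ADL are assigned an ANOVA with no visit or baseline term, although the mixed model already named in 11.6 would use the three-visit data better at almost no cost

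*Protocol*

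**What the plan says.** Section 11.6 of the Protocol gives Sub-Aim 2 this method: "Analysis of Variance (ANOVA) will be utilized to determine differences in continuous variables of physiological adaptation". For supervisor-rated occupational performance in Sub-Aim 3, "ANOVA will be utilized to determine differences in M-ADL scores between interventions". The section closes with a decision rule that follows all the aims: "A significant p-value of 0.05 will be used to assess main effects". CFT pass/fail, also in Sub-Aim 3, has its own method (Poisson regression with robust variance) and is outside this point.

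Other parts of the Protocol bear on the choice:

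- **Schedule (10.1, Study Evaluations).** Assessments are made "at three study time points: pre-, post-, and 3 months post-treatment".
- **Sub-hypothesis 2 (9.3).** Cardiovascular function is to improve "as measured by changes in heart rate variability (HRV) and estimated maximal oxygen consumption (est. VO₂ max) compared to the control condition". No visit is named.
- **Sub-hypothesis 3 (9.3).** Better performance is expected "after completion of treatment and 3 months post-treatment compared to the control condition".
- **Missing data (11.1).** "We will leverage the statistical power of multilevel modeling to handle missing follow-up data". The sentence is not limited to one aim.
- **Primary aim and Sub-Aim 1 (11.6).** Overall NSI change is analysed with a multilevel mixed-effect model that accounts for repeated measures, and Sub-Aim 1 takes a similar approach.

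**The concern.** The ANOVA has intervention as its only stated factor. The data have three visits per person, including a pre-treatment value that should predict the later ones. As worded, the plan does not say which visit is compared, whether baseline is used, or what happens to a participant who misses a follow-up. ANOVA ordinarily omits such a participant, whereas 11.1 says that multilevel modelling will deal with missing follow-up.

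Precision and retained data on the physiological and occupational outcomes are at stake. Section 11.5 allows for 20% attrition and says that 140 participants suffice for the secondary aims. M-ADL can lose more, because participants may refuse supervisor contact (10.1, Command Evaluation). Leaving the contrast open also means that it could be chosen after the data are seen.

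**Working it through.** **Inputs from the Protocol.** 70 per arm (11.4); 20% attrition, two-sided alpha 0.05, 85% power (11.5); three visits (10.1). Evaluable per arm: 70 × 0.8 = 56.

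**Assumptions, not in the Protocol.** Equal variance σ² at each visit; one correlation ρ between any two visits, taken as 0.5, 0.7 and 0.8, with 0.3 as a low case; equal arms at baseline, as randomization implies on average; the same effect d (in SD units) at both follow-ups.

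**The plan's own figure.** Section 11.5 gives no effect size or SD, so the 85% can only be solved backwards. By the normal formula, d = (1.960 + 1.036) × √(2/56) = 0.566; the exact t calculation gives 0.571. I use d = 0.566 below.

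**Variance at one follow-up visit, per participant:**

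- raw score: σ²
- change from baseline: 2(1 − ρ)σ²
- baseline-adjusted: (1 − ρ²)σ²

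The ratios to the adjusted comparison are 1/(1 − ρ²) for raw scores and 2(1 − ρ)/(1 − ρ²) = 2/(1 + ρ) for change scores.

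| ρ | raw ÷ adjusted | change ÷ adjusted |
|---|---|---|
| 0.5 | 1/0.75 = 1.33 | 2/1.5 = 1.33 |
| 0.7 | 1/0.51 = 1.96 | 2/1.7 = 1.18 |
| 0.8 | 1/0.36 = 2.78 | 2/1.8 = 1.11 |

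These ratios depend on neither d nor the number of participants.

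**Power with 56 per arm and d = 0.566,** from Φ(d/√(2v/56) − 1.96), where v is the variance above with σ² = 1:

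| ρ | raw | change | baseline-adjusted |
|---|---|---|---|
| 0.3 | 85% | 72% | 88% |
| 0.5 | 85% | 85% | 93% |
| 0.7 | 85% | 97% | 99% |
| 0.8 | 85% | >99% | >99% |

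The detectable difference at 85% power is 0.566 SD with raw scores. With baseline adjustment it is 0.566 × √(1 − ρ²) = 0.49, 0.40 and 0.34 SD at ρ = 0.5, 0.7 and 0.8.

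**Validity.** In 10,000 simulated trials per value of ρ (0.3 to 0.8) with no effect, the rejection rate was 0.046 to 0.053 for raw scores at one visit and 0.051 to 0.053 for change scores. Both keep the nominal 5%.

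**One further reading of the decision rule.** Suppose *main effects* meant the group effect of a repeated-measures ANOVA over all three visits. The tested effect would be (0 + d + d)/3 = 2d/3, with variance (1 + 2ρ)/3. Power would be 69%, 61% and 57% at ρ = 0.5, 0.7 and 0.8, with alpha still 0.05.

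**The case against.** The strongest reply is that the named test can be carried out correctly. An ANOVA of change scores by arm at each follow-up fits the words of 11.6 and the change wording of Sub-hypothesis 2. An ANOVA of M-ADL scores at each follow-up answers Sub-hypothesis 3 directly. Both hold their error rate. Using different methods for different aims is not in itself a contradiction, 11.1 refers the reader to 11.6 for the plan, and the choice of visit and covariates may be settled in an analysis plan that is not shown. The outcomes are also not primary: 9.3 calls them exploratory in one place and secondary in another.

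Most of this stands, and it rules out two stronger conclusions that a reader might draw:

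- **Inflated type I error.** If all three visits were pooled as independent rows, the true error would be 2(1 − Φ(1.96/√(1 + 2ρ))), or 17% to 22% at ρ = 0.5 to 0.8. Nothing in the Protocol says or implies such pooling.
- **A diluted effect.** The shrinkage to two thirds needs a repeated-measures ANOVA that averages in the pre-treatment visit. Section 11.6 names no visit factor, and in a one-factor ANOVA the main effect is simply the arm effect. Dilution is a possible reading, not the stated test.

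The reply does not remove the choice of method. Section 11.6 does more than leave detail open: it names ANOVA, which uses only participants with the visit in question and, in both valid forms, is less precise than a comparison adjusted for a baseline that is already collected. It also sits uneasily with the general statement on missing follow-up in 11.1.

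**Conclusion.** The point holds as an improvement in efficiency and clarity, not as a demonstration that the planned test is invalid. It covers the continuous Sub-Aim 2 outcomes and M-ADL only. Against a baseline-adjusted comparison, a per-visit ANOVA has 1.33 to 2.78 times the variance on raw scores and 1.33 to 1.11 times on change scores, for ρ from 0.5 to 0.8. It also loses every participant who lacks that visit.

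These ratios rest on an assumed common correlation and equal variances. The power figures rest also on an effect size solved back from the 85% and on 56 evaluable per arm, which may be too many for M-ADL given the option to refuse supervisor contact. No figure in the Protocol is shown to be wrong. The two-thirds dilution is worth closing off in the wording because the decision rule permits that reading, but it should not be reported as what the plan does.

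**What to change.** In section 11.6, for the continuous Sub-Aim 2 outcomes and M-ADL:

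1. Replace ANOVA with the multilevel mixed-effect model already named there for overall NSI change. Model the two follow-up values on baseline value, arm, visit and arm-by-visit, with participant as the repeated unit, and include every randomized participant with at least one follow-up value.
2. Test the arm difference at post-treatment and at 3 months.
3. In the closing decision rule, replace *main effects* for these outcomes with the arm difference at the stated visit.

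Leave the Poisson analysis of CFT pass/fail as it is. The cost is two or three sentences. No visit, measurement or participant is added, and the type of model is already planned. As with any such model, the handling of missing visits assumes that missingness depends only on what has been observed.

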Participants will be assessed for balance dysfunctions using the Bertec Balance master. This vestibular balance mechanism is designed to measure and treat balance impairments following an mTBI. During this assessment, participants will be secured to the balance platforms via straps with carabiners, which attach to a vest worn by the participant. Once the patient is properly secured, the balance test can begin by selecting the appropriate assessment such as motor control, mobility, and weight shifting. This assessment takes approximately 20 minutes to complete.

Participants will perform isometric strength test to assess the ability to produce force generated through the legs, hips, hands, and arms. The Isometric Midthigh Pull protocol will measure the force being exerted against an immobile object using a dynamometer instead of lifting heavy amounts of weight to determine strength. Participants will be asked to walk up to the racked barbell and resemble a deadlift position that's held at the midthigh. The barbell will be attached to an immobile object via straps and a dynamometer to measure the force being exerted when pulled. The Grip Strength protocol will measure maximal force generated through each hand using a handheld dynamometer. Participants will be asked to remain seated while holding the handheld dynamometer in a 90-degree position and squeeze as hard as possible when given the signal.

Participants will perform a mock Marine Corps Combat Fitness Test (CFT) as administered by study personnel. The CFT is composed of three specific tasks the SM must complete and will take approximately 20 minutes. Each test is scored independently and corrected for gender and age:

- 1) Run: SM completes an 880 yard run. Primary dependent measure is seconds to complete.
- 2) Lift: SM lifts a 30-pound ammunitions can (or equivalent) overhead from shoulder height. Dependent measure is max reps for two minutes.
- 3) Maneuverability: SM completes a simulated maneuver-under-fire event. This is a timed 300-yard shuttle run in which the SM completes a series of tasks: sprints, agility course, high crawl, low crawl, body drag, fireman carry, ammo can carry, push-ups and grenade throw. Dependent measure is seconds to complete.

Command Evaluation

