Maximal Aerobic Capacity (VO ₂ max)	Secondary Aim 2	VO ₂ max is a numeric representation of the maximum amount of oxygen that is usable by the body during intense exercise, reflecting the aerobic or cardiovascular fitness level of an individual. The Korr Cardio Coach Plus will be used to capture VO ₂ . The Korr Cardio Coach Plus has been shown to accurately measure submaximal and maximal VO ₂ (Dielic-Conwright, Jensky, Battaglia, McCauley, & Schroeder, 2009).
Balance	Secondary Aim 2	The Bertec Balance Master Smart Balance Manager will be used to asses balance dysfunction pre and post intervention. Patients are secured to the balance platforms via straps with carabiners which attach to a vest being worn by the patient. Once the patient is properly secured, the balance test can begin by selecting the appropriate assessment such as motor control, mobility, weight shifting, etc. The Bertec uses an encircled dome surrounding the balance platform, which projects a moving background giving patients the sensation that they are moving using virtual reality technology (Quintana et al., 2021).
Marine Corps Combat Fitness Test (CFT)	Secondary Aim 3	The CFT is composed of an 880 yard run, max repetitions of an overhead lift of a 30-pound ammunition can, and performance during an under-fire simulated event and completed by all Marines regardless of gender or age. A mock CFT will be proctored by study personnel at baseline, post-treatment, and three months post-treatment.
Military Activities of Daily Living (M-ADL)	Secondary Aim 3	The M-ADL is an evaluation survey which includes 18 items designed to assess performance of SMs by their direct supervisors
Ohio State University Traumatic Brain Injury Identification Method (OSU-TBI ID)		The OSU-TBI ID is a standardized procedure for eliciting a person's lifetime history of TBI via a 3-5 minute structured interview. The validity of the OSU TBI-ID is not based on a perfect accounting of a person's lifetime history of TBI, it is a means to estimate the likelihood that consequences have resulted from one's lifetime exposure

At any point in the study, will you request, use, or access health information in any form, including verbal, hard copy and electronic?

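### The CFT is analysed only as pass/not pass, although it is measured in seconds and repetitions at three visits; the claim that 140 participants suffice for the secondary aims does not follow for it

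*Protocol*

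**What the plan says.** Section 10.1 (Physical Assessments) describes three CFT events. Of the set it says "Each test is scored independently and corrected for gender and age". For the run, "Primary dependent measure is seconds to complete"; for the lift, "Dependent measure is max reps for two minutes"; the manoeuvre event is also timed in seconds. Section 10.2 adds "A mock CFT will be proctored by study personnel at baseline, post-treatment, and three months post-treatment". Sub-hypothesis 3 in section 9.3 reads "SAET participants will have improved locomotion and physical performance", with the CFT as the measure, after treatment and three months later.

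Section 11.6, Sub-Aim 3, gives one CFT analysis: "participants will be categorized as passing or not passing their CFTs", compared between arms as a prevalence ratio from Poisson regression with robust errors, introduced by "given >10% with passing CFTs". It names no analysis of times or repetitions.

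Section 11.5 bases the sample size on change in neurobehavioral symptoms (70 per arm, 85% power, two-sided 0.05, 20% attrition) and closes: "The 140 participants recruited will suffice to address the research question for secondary aims given the same parameters".

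**The concern.** The hypothesis concerns improvement and the declared measures are quantitative, but the planned comparison registers a gain only when it carries someone over the pass mark. The size of a change is not used. Elsewhere the protocol does otherwise: the NSI is analysed continuously with an 8-point threshold added, and the physiological outcomes and M-ADL scores go into ANOVA. Of the outcomes assigned a method in section 11.6, only the CFT is reduced to a threshold alone.

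If most controls pass, a real fitness gain could well go undetected, and section 11.5 would allow that null result to be read as adequately powered. The stake is limited: sections 9.3 and 10.2 call these aims exploratory, and the primary NSI analysis is unaffected.

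**Working it through.** **Inputs from the protocol (section 11.5).** 70 per arm, 20% attrition, two-sided alpha 0.05, power 85%. Completers per arm: 70 × 0.8 = 56.

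**Inputs assumed, because the protocol does not state them.** The standardised effect d, the control pass rate pc, the correlation between baseline and follow-up, and the correlation between events.

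**Step 1: the plan's own figure.** The 85% cannot be reproduced, since no effect size or SD is given. It can be turned round: d = (1.960 + 1.036) × √(2/56) = 0.566, or 0.571 with the noncentral t. So 140 participants give 85% power for a continuous outcome if d is about 0.57.

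**Step 2: the same shift cut at a pass mark.** Take one normal score, with passing meaning that it exceeds a mark. The SAET pass rate is pt = Φ(Φ⁻¹(pc) + d). Example: pc = 0.70 gives pt = Φ(0.524 + 0.571) = 0.863. Power is from the pooled two-proportion test with 56 per arm:

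| Control pass rate | d = 0.40 | d = 0.571 | d = 0.75 | d = 0.92 |
|---|---|---|---|---|
| 10% | 27% | 50% | 75% | 91% |
| 20% | 34% | 61% | 85% | 96% |
| 30% | 38% | 66% | 88% | 97% |
| 40% | 39% | 67% | 88% | 97% |
| 50% | 38% | 65% | 86% | 96% |
| 60% | 36% | 62% | 82% | 93% |
| 70% | 33% | 55% | 75% | 88% |
| 80% | 27% | 46% | 63% | 75% |
| 90% | 19% | 30% | 42% | 50% |
| **Same score kept continuous** | **56%** | **85%** | **98%** | **>99%** |

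The value 0.92 is the only effect size printed in the protocol (section 9.2, a meta-analysis of symptoms, not fitness). A Wald test of the log prevalence ratio, which is what unadjusted robust Poisson amounts to here, gives 27% to 66% at d = 0.571.

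**Step 3: what pass/fail would need.** For 85% power at d = 0.571, pass/fail needs 87.3 completers per arm at best (pc = 40%), 113.2 at 70% and 237.4 at 90%. Divided by 56, that is 1.56, 2.02 and 4.24 times as many. At a 90% control rate, universal passing in the SAET arm would still give only about 68% power with 56 per arm.

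**Step 4: what the baseline score adds.** Adjusting for baseline raises the effective d to d/√(1 − ρ²). At d = 0.571, continuous power becomes 88%, 93%, 96% or 99% for assumed ρ of 0.3, 0.5, 0.6 or 0.7.

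**Step 5: three events and one pass rule.** Suppose d = 0.571 on each event, correlation r between events, and passing judged on the sum. The sum then has d = 3 × 0.571/√(3 + 6r), which is 0.78 at r = 0.3 and 0.70 at r = 0.5.
- r = 0.3: pass/fail on the sum has 88% to 91% power at control rates of 20% to 50%. The sum kept continuous has 98%; one event alone, unadjusted, has 85%.
- r = 0.5: pass/fail on the sum has 80% to 83% at the same rates. The sum kept continuous has 96%.

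The loss is therefore established for a score against its own cut, not for a single event against a cut of the total.

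**The case against.** The strongest reply has four parts.

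- **Passing is the right endpoint.** Readiness is the trial's purpose, and passing a military fitness test expresses it directly. This stands as a reason to keep the pass rate. It is no reason to leave the declared measures unanalysed.
- **The power figures are conditional.** The d is back-solved from the symptom calculation, and the pass rates and correlations are assumed. This stands for the absolute values. The direction does not depend on them: for the same score, the continuous analysis had more power at every d from 0.40 to 0.92 and every control rate from 10% to 90% examined. An effect confined to people near the pass mark could behave differently.
- **The pass rule cannot be seen.** Section 11.6 refers to a Table 3 that is absent from the text at hand, so it is unknown whether passing means a total score or passing each event. This stands, and Step 5 shows that it matters. A reader might infer that dichotomising loses power against any continuous alternative; that goes too far, because pass/fail on a total can beat one unadjusted event.
- **A statistical analysis plan may add to this.** It could supply covariates or a continuous analysis, so silence on a baseline term is not in itself an error. But the protocol states the binary analysis and the sufficiency claim outright.

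Two further inferences are tempting. One is that the pass/fail analysis is bound to fail: at d = 0.75 it reaches at least 85% power for control rates of 20% to 50%. The other is that the protocol expects about 10% to pass: "given >10% with passing CFTs" reads as the condition for choosing robust Poisson, not as a forecast.

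**Conclusion.** The point holds in a limited form. The protocol collects quantitative CFT results at three visits and plans to analyse only whether participants pass. For the same roughly normal score with 56 completers per arm, a shift that gives 85% power continuously gives about 30% to 67% as pass/fail over control pass rates of 10% to 90%. A sample size set for a continuous symptom change therefore does not carry over to this endpoint on the same parameters. Sufficiency is unsupported rather than disproved, since a larger fitness effect with middling pass rates could rescue it and neither is stated. The change is worth making because it is cheap, but it concerns a secondary endpoint that the protocol also calls exploratory.

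**What to change.** **Section 11.6, Sub-Aim 3.** Analyse the CFT as a continuous outcome with the baseline value as covariate. Use the score on which passing is judged, or a composite of the three gender- and age-corrected events, and report the individual events alongside. Add a rank-based sensitivity analysis in which participants who cannot finish an event rank below all finishers. Keep the prevalence ratio of passing as the supportive readiness measure, which mirrors the protocol's treatment of the NSI and its 8-point threshold.

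**Section 11.5, last sentence.** Limit it to continuous outcomes with a standardised difference of about 0.57 (56 completers per arm), and state that power for the proportion passing the CFT is lower at the same effect.

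**Cost.** Protocol wording, a little more analysis work, a rule for unfinished events, and a slightly less favourable power statement. No new data, visits or participants.
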